#### Randomization and blinding

Eligible patients are randomly allocated in a 1:1 ratio to the 'individualized high PEEP' or 'low PEEP' strategy. The allocation sequence is computer–generated by an independent investigator using permuted blocks of different block sizes, with a maximum block size of eight and stratified per center and BMI ( $\leq$  30 vs. > 30 kg/m^2). Randomization is performed by local investigators patient–by–patient employing a dedicated, password protected, SSL–encrypted website.

At each site, at least two investigators are involved with the study. One investigator randomizes the patients immediately before surgery and is responsible for the trial intervention and data collection. A second investigator remains blinded for the randomization and is responsible for postoperative data

collection. The surgeon and patient are kept blind to the allocated ventilation strategy. Since PEEP can be adjusted at any time point upon the surgeons' request or because of concerns about patient's safety, and since patients do not profit from knowing to which group they are allocated to, unblinding is not applicable.

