#### Subgroup analysis

Treatment effects on incidence of PPC will be analyzed according to the following predefined subgroups: 1) age < 65 years  $vs \ge 65$  years; 2) body mass index < 30 kg/m^2 vs BMI  $\ge$  30 kg/m^2; 3) baseline SpO2 < 96% vs SpO2  $\ge$  96%; 4) moderate vs high risk for PPC according to the ARISCAT risk score (< 45 vs.  $\ge$  45); 5) duration of surgery < 3 hours  $vs \ge$  3 hours; and 6) planned destination to ICU or HDU vs ward. Analyses of heterogeneity of effects across subgroups will be performed with the use of treatment–by–subgroup term added to the primary model and will be presented in a forest plot.

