# Table 2 – List of proposed tables and figures

|               | Description   |
|---------------|---|
| Main paper    |   |
| Table 1       | Baseline Characteristics of the Included Patients   |
| Table 2       | Ventilation and Intraoperative Characteristics  |
| Table 3       | Primary and Secondary Outcomes  |
| Figure 1      | Participant Flow Diagram  |
| Figure 2      | Postoperative Pulmonary Complications in Prespecified Subgroups
A forest plot showing the absolute difference and two-sided 95% confidence intervals with p value for interaction calculated via a test for treatment-by-subgroup interaction in
the regression model. A solid line of reference in the number 1 and a dashed line of reference in the overall effect will be shown.  |
| Online Supple | ement   |
| eTable 1      | Rate of Missing Data A table showing the rate of missing data.  |
| eTable 2      | Additional Intraoperative Characteristics
A table showing additional intraoperative characteristics.   |
| eTable 3      | Rescue Therapies in Included Patients
A table showing the steps of rescue therapies in patients receiving rescue in each arm.  |
| eTable 4      | Protocol Deviations
A table reporting the protocol deviations in each arm.   |
| eTable 5      | Daily Assessment of Included Patients
A table showing characteristics over the first 5 days of follow-up.  |
| eTable 6      | Multiplicity adjustment for secondary outcome analyses
A table showing the observed p values for all the secondary outcomes and ordered from the lower until the higher and the corrected p values using a Holm–Bonferroni correction  |
| eTable 7      | Sensitivity Analyses for the Primary Outcome
A table showing the proposed sensitivity analyses for the primary outcome (count analysis, common effect test, average relative effect test and heterogeneity of treatment effect)  |

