| eFigure 1     | Characteristics of the Intervention
A, Line plot reporting the mean and 95% confidence interval of the driving pressure after intubation, after recruitment maneuver, during first and second hour of surgery and at the last hour by treatment group.
B, Bar plot reporting the mean difference in driving pressure between groups after intubation, after recruitment maneuver, during first and second hour of surgery and at the last hour.
C, Bar plot showing the titrated level of PEEP in the individualized high PEEP group.
D, Line plot showing the plateau pressure and driving pressure according to PEEP levels during the PEEP titration maneuver in the individualized high PEEP. |
| eFigure 2     | Level of PEEP in the Study Population
Histogram reporting the most used level of PEEP during the first five hours of the surgical procedure by treatment group.  |
| eFigure 3     | Tidal Volume, PEEP, Peak Pressure, Plateau Pressure, FiO 2 and SpO 2 During Surgery
Line graph reporting the mean and 95% confidence interval of the variables after intubation, after recruitment maneuver, during first and second hour of surgery and at the last
hour by treatment group.   |
| eFigure 4     | VAS Pain, Respiratory Rate, SpO 2 and Mean Arterial Pressure During the First Five Days of Follow-Up
Line graph reporting the mean and 95% confidence interval of the variables in the first five days of follow-up by treatment group.   |
| eFigure 5     | Patient Status in the First Five Days of Follow-Up  |

|           | Transition plot showing the status of the patients in the first five days of follow-up.   |
|-----------|---|
| eFigure 6 | Confidence Distribution for the Primary Outcome
Confidence distribution of the estimated absolute difference of the primary outcome of Individualized High PEEP versus Low PEEP constructed using a normal approximation.
A, The full confidence distribution of the estimated absolute difference, with the dashed vertical line indicating the median value and the area highlighted in tan indicating the
95% confidence interval. The orange area is related to an absolute difference greater than 0 (i.e., the intervention is associated with higher incidence of PPC vs standard care).
The dotted line at an absolute difference of 0 indicates no treatment effect. The figure demonstrates that the confidence probability that Individualized High PEEP is associated |

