# Table 4 (Table 2) – Ventilation and Intraoperative Characteristics

|   | Individualized
High PEEP
( n = XXX) | Low PEEP
(n = XXX) | Absolute Difference
(95% Cl) | p value |
|---|--|-----------------------|---------------------------------|----------------|
| Mean arterial pressure, mmHg                    | . ,  |                       |                                 |                |
| After intubation                                |  |                       |                                 |                |
| During first hour                               |  |                       |                                 |                |
| Last hour                                       |  |                       |                                 |                |
| Duration of anesthesia, min                     |  |                       |                                 |                |
| Duration of surgery, min                        |  |                       |                                 |                |
| Duration of surgery ≥ 180 min – no. (%)         |  |                       |                                 |                |
| Maintenance of anesthesia – no. (%)
Volatile |  |                       |                                 |                |
|   |  |                       |                                 |                |
| Epidural – no. (%)                              |  |                       |                                 |                |
| Thoracic  |  |                       |                                 |                |
| Lumbar  |  |                       |                                 |                |
| Neuromuscular monitoring – no. (%)              |  |                       |                                 |                |
| Residual paralysis at extubation– no. (%)       |  |                       |                                 |                |
| Paralysis reverted – no. (%)                    |  |                       |                                 |                |
| Temperature at the end of the surgery, °C       |  |                       |                                 |                |
| Fluids  |  |                       |                                 |                |
| Total intake, mL                                |  |                       |                                 |                |

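### The main-paper subgroup forest plot shows absolute differences but puts its solid reference line at 1 instead of 0, and its duration-of-surgery split is, as worded, post-randomisation and not labelled as such

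*SAP*

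**What the plan says.** In the SAP's Table 2, the entry for Figure 2 of the main paper begins "A forest plot showing the absolute difference and two-sided 95% confidence intervals", adds an interaction p value, and closes with "A solid line of reference in the number 1 and a dashed line of reference in the overall effect will be shown". The Subgroup analysis section confirms the scale: the treatment-by-subgroup term is "added to the primary model and will be presented in a forest plot". That primary model (Primary outcome section) is a binomial mixed model with identity link, reported as an absolute difference. For the same measure, the eFigure 6 entry in Table 2 says: "The dotted line at an absolute difference of 0 indicates no treatment effect".

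The Subgroup analysis section gives six predefined subgroups. The fifth reads "5) duration of surgery < 3 hours" against 3 hours or more, with no word such as planned or expected. The sixth reads "6) planned destination to ICU or HDU vs ward". Under Randomization and blinding the SAP says: "One investigator randomizes the patients immediately before surgery". The same cut appears in Table 4 as "Duration of surgery ≥ 180 min", among the ventilation and intraoperative characteristics compared between arms, and not in the baseline table.

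The BMI subgroup is below 30 against 30 and above, whereas the randomisation stratum is 30 and below against above 30.

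**The concern.** A reader of a forest plot judges each interval by whether it crosses the solid line. If that line is not at the null of the plotted measure, the figure misleads even when every number on it is right. On a percentage-point axis both possible misreadings favour the intervention:

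- An interval whose upper limit lies between 0 and +1 would seem to exclude no effect when it does not.
- An interval whose lower limit lies between 0 and +1 would seem compatible with no effect when it in fact excludes it on the side of harm.

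The duration split raises a different issue. Surgical time is observed after allocation. If the ventilation strategy affects it, the arm helps decide which stratum a patient falls into. The within-stratum contrasts and the interaction test are then no longer comparisons of randomised groups. Fixing the split in advance does not make the variable a baseline one, and the plan does not tell readers that this subgroup differs in kind from the other five.

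**Working it through.** **Null value by scale.** With equal risk p in both arms, the difference is p − p = 0 and the ratio is p / p = 1. The SAP's value of 1 can be reproduced only on a ratio scale. It cannot stand for the overall effect, which has its own dashed line. The SAP's table of modifications shows that the risk ratio of the 2020 plan was replaced by the absolute difference. A carry-over from that plan is a likely explanation, but it is an inference.

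**Inputs for size** (SAP, Sample size): 34% in the control arm, 27.2% in the experimental arm, 734 patients per arm. The planned difference is 27.2 − 34 = −6.8 points. The subgroup shares of one half and one quarter are assumptions.

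**Interval half-width.** v = 0.34 × 0.66 + 0.272 × 0.728 = 0.2244 + 0.1980 = 0.4224. SE = √(v / n per arm), half-width = 1.96 × SE.

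| Share of patients | n per arm | SE (points) | Half-width (points) | 1 point as share of half-width |
|---|---|---|---|---|
| All | 734 | 2.40 | 4.70 | 21% |
| Half | 367 | 3.39 | 6.65 | 15% |
| Quarter | 183.5 | 4.80 | 9.40 | 11% |

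**Chance that an interval contains exactly one of 0 and +1** (percentage-point axis, normal approximation, same SE under both scenarios). This is P(upper limit between 0 and 1) + P(lower limit between 0 and 1).

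| True difference | Half of patients | Quarter of patients |
|---|---|---|
| −6.8 points | 0.115 + 0.000 = 11.5% | 0.0754 + 0.0002 = 7.6% |
| 0 | 0.0229 + 0.0129 = 3.6% | 0.0149 + 0.0099 = 2.5% |

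For example, for half the patients at −6.8 the upper limit has mean −6.8 + 6.65 = −0.15 and SE 3.39. So P(0 to 1) = Φ(1.15 / 3.39) − Φ(0.15 / 3.39) = 0.633 − 0.518 = 0.115.

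On a proportion axis the line at 1 means a difference of 100 points. With 2% dropout (about 719 per arm), the expected interval for half the patients runs from about −0.135 to −0.001, and for a tenth from about −0.218 to +0.082. The line is far from both.

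**Duration split.** No arithmetic applies; the passages are set side by side. Randomisation comes immediately before surgery. Duration carries no qualifier, although the next item in the same list does say planned. The 180-minute row sits with the intraoperative variables. As worded, the split is therefore known only after randomisation.

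**BMI boundary.** Only patients at exactly 30 move between categories. Assuming normally distributed BMI with mean 25–29 and SD 4–6, they are 0.46–0.97% of patients (about 7–14 of 1,468) if BMI is kept to one decimal, and 4.6–9.6% if it is rounded to integers. The SAP does not state the precision.

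**The case against.** The strongest reply on the reference line concerns weight. It is one digit in a list of proposed figures, the analysis text is right, and the interaction p values printed on the plot are unaffected. The percentages above hold only on a percentage-point axis and for the assumed subgroup sizes and effects. On a proportion axis the mistake would be obvious as soon as the figure was drawn. All of this is true, and it limits the point to display and reading. It does not remove the contradiction in a pre-specified main-paper figure, which should not depend on silent correction.

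On duration, the protocol is not at hand and may define a planned duration. Surgeons are blinded to allocation, which makes an effect of the arm on operating time less likely. Table 4 will compare both duration in minutes and the 180-minute split between arms, so a gross effect would be visible. These facts lessen the concern, but they do not turn an observed duration into a baseline variable. If the protocol does mean planned duration, the SAP wording needs aligning with it.

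On BMI, the cut at 30 and above is used consistently for the subgroup and the baseline table, and redefining a subgroup this late has its own cost. That is a fair reason to treat the change as optional.

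**Conclusion.** The reference line is wrong as written; this follows from the SAP's own text and rests on no assumption. Its effect is confined to how Figure 2 is read. On a percentage-point axis the apparent null moves by 1 point, about 15% of the interval half-width for a subgroup of half the patients and 11% for a quarter. These figures use the design event rates, 734 per arm without dropout, and a normal approximation.

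The duration split is, as worded, post-randomisation and unlabelled. Any bias cannot be sized from the SAP and is zero if the arm does not affect duration, so what is warranted is a label and not a claim of demonstrated bias. The BMI boundary mismatch is real but minor, and stratification balance is essentially kept.

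**What to change.** 1. In the Figure 2 entry of Table 2, put the solid reference line at 0 and state whether the axis is in percentage points or proportions. This changes one character and adds a few words.
2. In the Subgroup analysis section and in Figure 2, label the duration split as post-randomisation and descriptive, set apart from the other five subgroups. If an expected duration was recorded before randomisation (the SAP does not show one), it could be used instead. Labelling takes one sentence and no new data.
3. Optionally, define the BMI subgroup and the matching row of the baseline table by the randomisation stratum (30 and below against above 30).

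The SAP was closed in January 2024 and updated in January 2025, so item 2, and item 3 if adopted, should be entered with a date in the table of modifications.

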# Table 3 (Table 1) – Baseline Characteristics of the Included Patients

|  | Individualized High PEEP
(n = XXX) | Low PEEP
(n = XXX) |
|--|---------------------------------------|-----------------------|
| Systolic blood pressure, mmHg                  |                                       |                       |
| Mean arterial pressure, mmHg                   |                                       |                       |
| Respiratory rate, breaths/min                  |                                       |                       |
| Temperature, °C                                |                                       |                       |
| SpO 2 , %                           |                                       |                       |
| SpO 2 < 96% - no. (%)               |                                       |                       |
| Preoperative chest X-ray – no. (%)             |                                       |                       |
| Infiltrates                                    |                                       |                       |
| Pleural effusion                               |                                       |                       |
| Atelectasis                                    |                                       |                       |
| Preoperative laboratory                        |                                       |                       |
| Hemoglobin, g/dL                               |                                       |                       |
| Creatinine, mg/dL                              |                                       |                       |
| Data are median (quartile 25th - quartile 75th | ) or N / total (%)                    |                       |

## Table 3 (Table 1) – Baseline Characteristics of the Included Patients

in (quartile 25th - quartile 75th) or N / total (%).

Abbreviations: PEEP is positive end-expiratory pressure; ARISCAT is The Assess Respiratory Risk in Surgical Patients in Catalonia; ASA is American Society of Anesthesiology; COPD is chronic obstructive pulmonary disease; SpO2 is pulse oximetry.

\* Cessation more than 3 months.

\*\* A patient can have more than one.

|                                       | Individualized
High PEEP     | Low PEEP
(n = XXX) | Absolute Difference
(95% Cl) | p value |
|---------------------------------------|---------------------------------|-----------------------|---------------------------------|----------------|
| Poeruitmont managiver no (%)          | $(n - \lambda \lambda \lambda)$ |                       |                                 |                |
| Number of recruitment maneuvers       |                                 |                       |                                 |                |
| Lowest AP during PEEP titration cmH2O |                                 |                       |                                 |                |
|                                       |                                 |                       |                                 |                |
| After intubation                      |                                 |                       |                                 |                |
| During first hour                     |                                 |                       |                                 |                |
|                                       |                                 |                       |                                 |                |
|                                       |                                 |                       |                                 |                |
| After intubation                      |                                 |                       |                                 |                |
| During first hour                     |                                 |                       |                                 |                |
|                                       |                                 |                       |                                 |                |
|                                       |                                 |                       |                                 |                |
| After intubation                      |                                 |                       |                                 |                |
| During first hour                     |                                 |                       |                                 |                |
|                                       |                                 |                       |                                 |                |
|                                       |                                 |                       |                                 |                |
| After intubation                      |                                 |                       |                                 |                |
| During first hour                     |                                 |                       |                                 |                |
| Last hour                             |                                 |                       |                                 |                |
|                                       |                                 |                       |                                 |                |
| After intubation                      |                                 |                       |                                 |                |
| During first hour                     |                                 |                       |                                 |                |
|                                       |                                 |                       |                                 |                |
| Last hour                             |                                 |                       |                                 |                |
| After intubation                      |                                 |                       |                                 |                |
| During first hour                     |                                 |                       |                                 |                |
| Last hour                             |                                 |                       |                                 |                |
| FiOn                                  |                                 |                       |                                 |                |
| After intubation                      |                                 |                       |                                 |                |
| During first hour                     |                                 |                       |                                 |                |
| Last hour                             |                                 |                       |                                 |                |
| SpO2 %                                |                                 |                       |                                 |                |
| After intubation                      |                                 |                       |                                 |                |
| During first hour                     |                                 |                       |                                 |                |
| Last hour                             |                                 |                       |                                 |                |
| etCO 2 mmHa                |                                 |                       |                                 |                |
| After intubation                      |                                 |                       |                                 |                |
| During first hour                     |                                 |                       |                                 |                |
| Last hour                             |                                 |                       |                                 |                |

